2. Critical care bed days (if yes)	Number (days from first post-operative day to day of discharge from critical care. If the patient has not been discharged prior to the end of 30-day follow-up, enter '31').	
3. Postoperative haemoglobin	Not applicable / Available (day 0-1, day 1-3, day 4-6, last prior to discharge) If available, please state value in grams/litre	
4. Postoperative interventions for anaemia	None / iron supplementation / Tranexamic acid / RBC transfusion (If yes: 1, 2, 3, 4, ≥5 units)	
5. Cardiovascular complications within 30 days	None / Myocardial infarction / Myocardial injury / Non-fatal cardiac arrest / Coronary revascularisation / Pulmonary embolism (symptomatic non-fatal / asymptomatic) / Deep venous thrombosis (proximal / distal; if either symptomatic / asymptomatic) / New onset Atrial fibrillation / Stroke (select all that apply) *see Appendix D for definitions Please indicate the POD of the event(s) selected.	• Clinical notes • PACS software
6. Bleeding complications within 30 days	None / Major bleeding / Clinically relevant non-major bleeding *see Appendix D for definitions	
7. Post-operative length of stay	Number (days between from the first post-operative day to day of discharge. If the patient has not been discharged prior to the end of 30-day follow-up, enter '31').	
8. Highest 30-day complication grade	None / Clavien-Dindo Grade I-V (see Appendix D for the full 7-point Clavien-Dindo scale). If grade V, was death cardiac, PE or non-cardiac? (see Appendix D for definitions)	
9. 30-day Reoperation	Yes / No	
10. 30-day Readmission	Yes - planned / Yes- unplanned / No (this applies if patient had died during initial admission) If yes: what is the grade of complication (none, grade I, grade II, grade III, grade IV, grade V)	
11. 30-day postoperative COVID status	None / Preoperative / Postoperative If preoperative: are you still symptomatic (yes/no) and were you vaccinated (no / partial / full)	
12. Haemoglobin on readmission	Not available / Available If available, please state value in grams/litre	
13. Interventions for anaemia at readmission	None / iron supplementation (Oral / Intravenous), blood transfusion (If yes: 1, 2, 3, 4, ≥5 units)	
14. Postoperative outpatient VTE prophylaxis duration	Number (days of pharmacological VTE prophylaxis the patient was discharged home with)	

15. Postoperative outpatient VTE prophylaxis	None / Low molecular weight heparin / Direct oral anticoagulants / Warfarin *If DOAC was selected, was this dabigatran, rivaroxaban, apixaban, edoxaban or betrixiban?	
--	--	--

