
1. Early recognition of patients needing specialist postoperative input
	
Royal College of Anaesthetists: Guidelines for the Provision of Anaesthesia Services 2019²⁵
 
 • Provision of Postoperative Care Recommendation 3.23: Mechanisms for the early recognition of patients requiring specialist postoperative input from geriatrician-led services and/or critical care should be developed. These should include patients at risk of or presenting with delirium, multiple medical complications, functional decline or complex discharge planning.

2. Postoperative intravenous iron therapy is indicated in patients with iron deficiency anaemia
	
International consensus statement on Postoperative Anaemia after Major Surgery 2018²⁶
 
 • Postoperative iron therapy: Should postoperative iron therapy be indicated, i.v. formulations are recommended

3. Extended pharmacological VTE prophylaxis is indicated in patients at high VTE risk after major abdominal or pelvic surgery
	
National Institute of Clinical Excellence: Venous thromboembolism in over 16s: reducing the risk of hospital-acquired deep vein thrombosis or pulmonary embolism (NG89) 2018
 
 • Consider extending pharmacological VTE prophylaxis to 28 days postoperatively for people who have had major cancer surgery in the abdomen.

Methods

1. Summary

A prospective, multicentre, study will be delivered by STARSurg Collaborative & EuroSurg Collaborative across Europe. Mini-teams of up to four collaborators (medical students and at least one doctor) per speciality group per data collection period will prospectively collect data over a continuous 14-day period at each participating centre. This will be on consecutive patients undergoing major abdominal surgery, with follow-up to 30 postoperative days. All mini-teams should be supervised by a consultant in surgery.

2. Study Aims:

- **Primary Aim:** To audit compliance to pre-, intra-, and postoperative audit standards in reducing risk of postoperative cardiovascular complication.

- **Secondary Aims**
 - To characterise rates and risk factors associated with postoperative cardiovascular complications following major abdominal surgery in Europe.
 - To explore the association of pre-operative and postoperative anaemia with postoperative cardiovascular complications and short-term outcomes (length of stay, readmission and 30-day mortality).

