 - Staged with a planned return for reoperation (such as but not limited to damage control laparotomy or burns surgery) OR
 - Change in operative plan such that during the first procedure it is determined that a reoperation is necessary, even if the patient was enrolled preoperatively
- **Return to theatre:** Each individual patient should only be included in the study *once*. Patients returning to theatre due to complications following earlier surgery can be included, as long as their indexed procedure has not already been included in the CASCADE audit.

You should collect data on consecutive patients operated at your centre during the data collection period. This means that all eligible patients should be included.

Strategies to identify consecutive eligible patients could include:

- *Daily review of elective theatre lists.*
- *Daily review of handover sheets/ emergency admission and ward lists.*
- *Daily review of theatre logbooks (both elective and emergency).*

6. Covariates:

Data will be collected on audit standards and confounding factors for risk-adjusted analyses. These include age, sex, ethnicity, body mass index, American Society of Anaesthesiologists (ASA) grade, relevant comorbidities, smoking status, anticoagulant or antiplatelet use, preoperative blood test values, and preoperative anaemia management. Variables including operative urgency, operative procedure, operative contamination, use of tranexamic acid, intraoperative blood transfusions used, haemoglobin level at transfusion, duration of procedure and post-operative iron therapy will also be collected. Without appropriately adjusting for risk factors, it is likely that any findings would be biased and unable to be appropriately analysed on a national scale. A full list of required data fields is available in **Appendix B**, and on the REDCap database.

7. Outcome Measures and Follow-up:

Primary outcome measure:

- Rates of compliance to pre-, intra-, and postoperative audit standards in reducing risk of postoperative cardiovascular complication.

Secondary outcome measures:

- Incidence of postoperative cardiovascular complications within 30-days of surgery according to the Standardized Endpoints for Perioperative Medicine (StEP) cardiovascular.¹³ (see **Appendix D: Definitions of Key Outcomes**).
- 30-day postoperative blood transfusion rates
- 30-day complication rates defined according to the Clavien-Dindo classification (see **Appendix D: Definitions of Key Outcomes**)

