Based on previous STARSurg and EuroSurg studies, CASCADE is anticipated to include around 300 centres in Europe. With consideration to recent figures provided by previous STARSurg and EuroSurg studies, it has been estimated that, on average, ten patients will undergo surgery per week at each participating centre. Therefore, a sample of approximately 6000 patients is anticipated. No surgeon-, hospital- or country-specific comparisons will be performed. Further secondary analyses may be performed at the Study Management Group discretion.

10. Local Project Registration:

At European centres, if the option is available, this project may be registered as clinical audit, quality improvement project or service evaluation. Alternatively, it may be necessary to obtain formal ethical approval. It is the responsibility of the local mini-team at each site ensure that the study is registered appropriately, according to local regulations. CASCADE should be registered in the UK and ROI as a clinical audit. It is the responsibility of the local mini-team at each site to identify a local consultants in surgery, anaesthesia or critical care to supervise them and ensure registration.

Confirmation that ethical review is not required for CASCADE within the UK is available in **Appendix F**. Examples of audit registration forms can be found at the online project hub. When registering CASCADE as a clinical audit you can emphasis that:

- CASCADE is a national audit, and all data collected will measure current practice.
- No changes to normal patient pathways/ treatment will be made.
- All CASCADE data will be collected and stored online through a secure server running the

Research Electronic Data Capture (REDCap) web application.²⁸ REDCap allows collaborators to enter and store data in a secure system. Collaborators will be given secure REDCap project server login details, allowing secure data storage on the REDCap database.

Collaborators in the UK should seek their trust's Caldicott Guardian's permission to submit data to the REDCap system. **No data should be uploaded to REDCap prior to written approval from the Caldicott Guardian.** No patient identifiable information (e.g. NHS numbers) should be uploaded or stored on the REDCap database without explicit permission from the trust's Caldicott Guardian. All data should be handled in accordance with national and local data governance policies.

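### Postoperative haemoglobin windows overlap at day 1 and carry no sampling day, so a reading cannot be ordered against an event in the same window and the postoperative-anaemia association could be reverse causation

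*Protocol*

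**What the plan says.** Appendix B, Post-operative Data Fields, item 3, asks for a haemoglobin value in g/L in each of four windows: "day 0-1, day 1-3, day 4-6, last prior to discharge". The Appendix A form repeats the same windows. Neither asks for the day or date of the sample.

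Section 2 gives as a secondary aim "To explore the association of pre-operative and postoperative anaemia with postoperative cardiovascular complications and short-term outcomes", the latter being length of stay, readmission and 30-day mortality. Section 7 defines the cardiovascular outcome as "Incidence of postoperative cardiovascular complications within 30-days of surgery", with no interval after the haemoglobin reading.

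On event timing, Appendix B item 5 says of cardiovascular complications: "Please indicate the POD of the event(s) selected". The Appendix A form lists the same complications but shows no entry for that day. Bleeding (item 6) is recorded by category only, "None / Major bleeding / Clinically relevant non-major bleeding". Death appears in item 8 as Clavien-Dindo grade V with its cause but no day. Length of stay (item 7) is counted as "days between from the first post-operative day to day of discharge".

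The protocol does not say which reading defines postoperative anaemia, or that the reading must precede the event.

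**The concern.** To read postoperative anaemia as a risk factor for a complication, the anaemia must have been measured first. The readings run up to discharge, while complications count from surgery. A complication can itself lower a later haemoglobin value, through bleeding, anticoagulation, repeated sampling or fluids. Such a value, used as exposure, reverses cause and effect.

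The record is too coarse to rule this out in every case:

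- A sample taken on day 1 fits two windows, so centres can code the same sample differently.
- A reading and an event in the same window have no order.
- Bleeding and death have no day, so neither can be placed relative to any reading.

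An analysis plan can choose which reading to use. It cannot restore a sampling day that was never collected.

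**Working it through.** **The plan's own figure.** The only planning number is the sample size. Section 9 says "CASCADE is anticipated to include around 300 centres in Europe" and "ten patients will undergo surgery per week at each participating centre", and each collection period is 14 days: 300 × 10 × 2 = 6000, as stated. The point below does not depend on it.

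**What can be ordered with the fields as they stand.**

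| Reading | Cardiovascular events certain to come later | Not orderable |
|---|---|---|
| Day 0-1 | Day 2 onward | Days 0-1 |
| Day 1-3 | Day 4 onward | Days 1-3 |
| Day 4-6 | Day 7 onward | Days 4-6 |
| Before discharge | After discharge | Events around the last sample, dated only through length of stay |

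**Illustration under a true null.** None of these inputs is in the documents: haemoglobin mean 115 and between-patient SD 15 g/L, measurement SD 4 g/L, anaemia below 110 g/L, time to event exponential with mean 4 days, mean stay about 7 days, and a fall of 5 or 10 g/L in readings after an event. Haemoglobin has no effect on events.

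The SD of a single reading is √(15² + 4²) = 15.52.

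- Anaemic without a prior event: Φ((110 − 115)/15.52) = 0.374, odds 0.597.
- Anaemic after an event: 0.500 for a 5 g/L fall, 0.626 for a 10 g/L fall.

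If a share f of events precedes the reading, the proportion anaemic among patients with an event is p = (1 − f) × 0.374 + f × (0.500 or 0.626), and the odds ratio is [p/(1 − p)]/0.597.

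- **Discharge reading.** f is about 0.82. For 5 g/L, p = 0.477 and the odds ratio is 0.912/0.597 = 1.53. For 10 g/L, p = 0.581 and it is 1.384/0.597 = 2.32.
- **Day 0-1 reading, all events counted.** With samples split evenly over days 0 and 1, f = [(1 − e^−0.25) + (1 − e^−0.5)]/2 = 0.307. The odds ratio is 1.18 for 5 g/L and 1.38 for 10 g/L.
- **Day 0-1 reading, events from day 2 only.** f = 0, so the odds ratio is 1.00.

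Simulation with these inputs (6000 patients, 300 runs) agrees: 1.53 and 2.32 for the discharge reading, 1.17-1.18 and 1.38 for day 0-1 with all events, and 1.00-1.02 with the landmark. The lowest of the day 0-1, day 1-3 and discharge values gave 1.39 and 2.05. Event rates of 5% and 25% gave nearly the same results, as expected, because p is conditional on having an event. With no fall after an event, every odds ratio was about 1.0.

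A second simulation used other assumptions (mean 108, SD 14 g/L, anaemia below 100 g/L, median event day 3). It gave 1.5 and 2.3 for the day 4-6 reading and 1.6 and 2.5 for the discharge reading.

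**How many events the missing sampling day affects.** Under the same exponential timing, the share of events falling inside each window is:

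- Day 0-1: 1 − e^−0.5 = 39%
- Day 1-3: e^−0.25 − e^−1 = 41%
- Day 4-6: e^−1 − e^−1.75 = 19%

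These events cannot be ordered against a reading from the same window. A sampling day would order those that fall on a different day from the sample.

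**The case against.** A reader might infer that the protocol plans to relate late readings to earlier complications, so that the association is bound to be spurious. The documents do not support this. Section 2 speaks only of exploring an association. Section 9 gives no model, no definition of anaemia and no choice among the four readings. Which reading to use, and whether to apply a landmark, may properly sit in the analysis plan, which is not shown.

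A reader might also infer from the Appendix A form that event days are not collected. That does not hold either. Section 6 names Appendix B as the full list of required fields, and Appendix B asks for the postoperative day of each cardiovascular event. With that day, the pairings in the table remove reverse causation for these events without any haemoglobin date.

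The size is open to challenge too. The fall after an event is assumed, and nothing in the documents shows that new atrial fibrillation or an asymptomatic thrombosis lowers haemoglobin. Transfusion after an event could raise it. Nor does the argument reach the whole aim: preoperative anaemia precedes surgery, and readmission and death follow the index-stay readings.

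All of this stands, and it limits the point to data collection. The day-1 overlap, the unordered readings and events within a window, and the undated bleeding and deaths remain whatever the analysis plan says. The form is also a practical risk: collaborators working from it see no event-day entry, and it refers them to an Appendix X, although the dictionary is Appendix B.

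**Conclusion.** The point holds as a data-collection fault with a conditional consequence. Day-1 samples can be coded in either of two windows, and a reading cannot be ordered against an event in its own window. The association with cardiovascular complications could be reverse causation if readings taken after the event enter as exposure.

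Under the assumed inputs, the spurious odds ratio is about 1.4 to 1.6 for a 5 g/L fall and 2.0 to 2.5 for 10 g/L with late, lowest or discharge readings. It is about 1.2 to 1.4 for the day 0-1 reading if all events count, and about 1.0 with a landmark. The early reading alone is therefore not enough; the landmark is what removes the bias. The aim is secondary and exploratory, but the change is small and the missing days cannot be recovered by analysis.

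**What to change.** 1. Make the windows non-overlapping (0-1, 2-3, 4-6, last before discharge) and record the postoperative day of each haemoglobin value.
2. Add the postoperative day of cardiovascular events to the Appendix A form so that it matches Appendix B, and add the day of death.
3. State that only readings taken before the event count as exposure. For example, use the day 0-1 value with events from day 2 onward, or pair each later window with events after it closes (2-3 with day 4 onward, 4-6 with day 7 onward). Patients who have had the event or died by the landmark leave that analysis.
4. Use the discharge value only for post-discharge outcomes such as readmission.

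The cost is one extra form field per reading, a form correction and a sentence of analysis wording. With the day 0-1 landmark, events on days 0-1 leave this association analysis (39% of events under the timing assumed above) but stay in the incidence estimate. If data have already been collected on the present form, the window pairings in the table can still be used wherever the event day was entered; the order within a window cannot be restored.

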2. Preoperative scoring tools should be used to risk stratify patients	
ERAS for gastrointestinal surgery: consensus statement for anaesthesia practice²⁴
 
 • Preoperative risk scoring: Preoperative scoring tools and functional capacity tests can be used to identify patients at risk of complications and to stratify perioperative risk 
American College of Cardiology (ACC) / American Heart Association (AHA) Clinical Practice Guideline²²
 
 • Preoperative risk scoring: A validated risk-prediction tool can be useful in predicting the risk of perioperative major adverse cardiovascular events in patients undergoing noncardiac surgery
3. Pre-operative Electrocardiogram (ECG)	
American College of Cardiology (ACC) / American Heart Association (AHA) Clinical Practice Guideline²²
 
 • Preoperative ECG: Pre-operative ECG is recommended for patients who have risk factor(s) and are scheduled for intermediate- or high-risk surgery.
4. Cardiopulmonary exercise testing for high-risk patients	
Royal College of Anaesthetists: Guidelines for the Provision of Anaesthesia Services 2021²³
 
 • Pre-operative Assessment and Preparation Recommendation 2.2: Cardiopulmonary exercise testing or functional assessment for high-risk patients should be carried out.
5. Preoperative iron supplementation in iron-deficiency anaemia	
National Institute of Clinical Excellence: Blood Transfusion Quality Standard (QS138) 2016
 
 • Iron supplementation: People with iron-deficiency anaemia who are having surgery are offered iron supplementation before and after surgery.

Intra-operative Standards	

1. WHO Surgical Safety Checklist should be used for all procedures.
	
Royal College of Anaesthetists: Guidelines for the Provision of Anaesthesia Services 2021²³
 
 • Pre-operative Assessment and Preparation Recommendation 12.50: The WHO's Surgical Safety Checklist should be used and is fully endorsed by the RCoA as the instrument for promoting team working and patient safety.
Post-operative Standards	

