Appendix B: Data Dictionary

Pre-operative Data Fields	Required data (definition / comment)	Suggested source(s)
1. Patient age	Years (whole years at the time of operation)	– Clinical letters / notes
2. Patient sex	Male / Female	– Clinical letters / notes
3. Patient body mass index (BMI)	kg/m² (record to two decimal places)	– Drug charts – Clinical letters / notes
4. Patient ASA grade	Grade I-V (Full ASA classification available at: https://www.asahq.org/resources/clinical-information/asa-physical-status-classification-system)	– Anaesthetic notes
5. Smoking status	Current (≤6 weeks, >6 weeks), Previous, Never	– Admissions clerking – Clinical notes
6. Clinical Frailty scale	1-3 / 4-6 / 7-9 (Full Clinical frailty scale available at: https://www.dal.ca/sites/gmr/our-tools/clinical-frailty-scale.html)	– Admissions clerking – Clinical notes
7. History of cardiovascular disease	Yes (myocardial infarction, angina, congestive cardiac failure, TIA/stroke, hypertension, peripheral vascular disease, atrial fibrillation, VTE, pulmonary embolism) / No If congestive cardiac failure, what is the NYHA: I / II / III / IV	– Admission clerking – Anaesthetic notes – Outpatient letters
8. History of respiratory disease	None / Dyspnoea on exertion or CXR (mild COPD) / Dyspnoea limiting exertion to <1 flight or CXR moderate COPD / Dyspnoea at rest/rate >30 at rest or CXR (fibrosis or consolidation)	
9. History of COPD	Yes / No	
10. History of chronic kidney disease	Yes (I / II / IIIA / IIIB / IV / V) / No	
11. History of liver cirrhosis	Yes / No	
12. History of diabetes mellitus	Yes - Type I / Yes - Type II (diet controlled, tablet controlled, insulin controlled) / No	
13. Active cancer and/or cancer treatment	Yes / No	
14. Inflammatory bowel disease	Yes / No	
15. Previous history of VTE	Yes / No	
16. Management of iron-deficiency anaemia	None / Preoperative iron supplementation / Tranexamic acid / RBC transfusion (If yes: 1, 2, 3, 4, ≥5 units)	
17. Preoperative treatment	Yes (Aspirin, ACEi/ARB, β-blocker, α ₂ agonist, rate controlling CCB, DHP CCB) / No If yes, was medication stopped preoperatively? (No / Yes, stopped preop only / Yes, stopped preop & postop)	– Clinical letters / notes PACS software
18. Preoperative therapeutic anticoagulation	Yes (Low Molecular Weight Heparin (LMWH), Warfarin, Direct acting oral anticoagulants (DOACs)) / No	– Clinical letters / notes PACS software

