19. Pre-admission blood tests	Haemoglobin (grams / litre) / Albumin (grams / litre) / Creatinine (ml / min) *Include blood tests taken within the 90 days prior to operation. If multiple blood tests have been taken during this period, record the lowest value. If no pre-admission blood tests are available, please record this as 0.	– Pathology systems
20. Admission blood tests	Haemoglobin (grams / litre) / White cell count (x10 ⁹ / l) / Albumin (grams / litre) / Sodium (mmol/l) / Potassium (mmol/l) / Urea (mmol/l) / Creatinine (ml / min)	– Pathology systems

	*Include the first blood test results from this admission. Only include blood tests taken before surgery	
21. Admission observations	Pulse rate (bpm) / Systolic blood pressure (mmHg) / Glasgow coma scale	–
22. Pre-operative assessment	If elective: Yes (pre-admission anaesthetic assessment clinic) / No. If yes: Did this include pre-operative cardiopulmonary exercise testing (Yes - VO ₂ peak, AT / No). If emergency: Yes (inpatient perioperative or elderly medicine, including physician or nurse specialist) / No	– Clinical letters / notes
23. Preoperative investigations	None / ECG (normal / abnormal) / Echocardiography (LVEF, %) / Coronary angiography	–
Abbreviations: ASA = American Society of Anaesthesiologists; Hb = Haemoglobin; LVEF = Left Ventricular Ejection Fraction PACS = Picture Archiving and Communication.		

Intra-operative Data Fields	Required data (definition / comment)	Suggested source(s)
1. Prior Operations	1 / 2 / >2	
2. Operative urgency (NCEPOD Classification of Intervention)	Immediate (Immediate life, limb or organ-saving intervention - resuscitation simultaneous with intervention. Normally within minutes of decision to operate). Urgent (Intervention for acute onset or clinical deterioration of potentially life-threatening conditions, for those conditions that may threaten the survival of limb or organ, for fixation of many fractures and for relief of pain or other distressing symptoms. Normally within hours of decision to operate) Expedited (requiring early treatment where the condition is not an immediate threat to life, limb or organ survival. Normally within days of decision to operate). Elective (Intervention planned in advance of routine admission to hospital).	– Operative note – Admissions clerking
3. Primary indication	Malignant / Benign If malignant: Primary only / nodal metastases / Distant metastases	– Operative note. – Clinical notes. – Theatre records.

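### Two of the nine audit standards in the primary outcome cannot be scored as defined: the index-admission form omits the route of iron, and no field records iron-deficiency status

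*Protocol*

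**What the plan says.** Methods section 7 of the protocol defines the primary outcome as "Rates of compliance to pre-, intra-, and postoperative audit standards in reducing risk of postoperative cardiovascular complication". The Audit Standards tables list five pre-operative, one intra-operative and three post-operative standards. Two of them concern iron:

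- Pre-operative standard 5 rests on this statement: "People with iron-deficiency anaemia who are having surgery are offered iron supplementation before and after surgery".
- Post-operative standard 2 is headed "Postoperative intravenous iron therapy is indicated in patients with iron deficiency anaemia". The recommendation cited beneath it reads "Should postoperative iron therapy be indicated, i.v. formulations are recommended".

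Methods section 6 presents Appendix B as the full list of required fields. The fields that bear on these standards are:

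- Pre-operative item 16, management of iron-deficiency anaemia: "None / Preoperative iron supplementation / Tranexamic acid / RBC transfusion".
- Post-operative item 4, for the index admission: "None / iron supplementation / Tranexamic acid / RBC transfusion". Appendix A labels this field 'IDA mx'; Appendix B labels it as interventions for anaemia in general.
- Post-operative item 13, for readmitted patients only: "None / iron supplementation (Oral / Intravenous), blood transfusion".
- Blood tests. Before admission: "Haemoglobin (grams / litre) / Albumin (grams / litre) / Creatinine (ml / min"). On admission: haemoglobin, white cells, albumin, sodium, potassium, urea and creatinine. After surgery: haemoglobin only, at up to four times.

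**The concern.** A compliance rate needs to know who the standard applies to and who met it. For post-operative standard 2 the distinguishing feature is the route, and the index-admission field does not ask for it. For both standards the eligible group is patients with iron-deficiency anaemia, and nothing on the form identifies them. A patient without the condition and a patient who has it but is untreated both produce 'None', yet the second is the case that the audit exists to find.

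This is a gap in data capture, not in analysis. An analysis plan can choose among recorded variables but cannot create route or iron status afterwards. The completeness rule in Methods section 11 will not reveal the gap, because 'None' is a complete entry. Going back to the source later is also hard: under Methods section 8, paper copies are destroyed after upload. Centres must present their results locally (Methods section 4), so misclassified failures would be fed back to clinical teams.

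**Working it through.** **The plan's own figures.** The sample size reproduces: 300 centres x 10 patients per week x 2 weeks = 6000. The point does not depend on it. The count of standards is 5 + 1 + 3 = 9, of which 2 concern iron (2/9 = 22%).

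**What each standard needs, set against what is collected.**

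| | Pre-operative standard 5 | Post-operative standard 2 |
|---|---|---|
| Denominator needed | Patients with iron-deficiency anaemia | Patients with iron-deficiency anaemia (heading) |
| Denominator recorded | No iron marker or diagnosis; haemoglobin only | The same |
| Numerator needed | Iron offered before and after surgery; no route named | Intravenous iron |
| Numerator recorded | Iron given: item 16 (before), item 4 (after) | Iron given, without route (item 4) |

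Across Appendices A and B, 0 fields hold an iron marker or a yes/no diagnosis of iron deficiency. Route is recorded in 0 of the 2 index-admission iron fields and in the 1 readmission iron field.

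**What haemoglobin can do.** Crossing 'None' with haemoglobin removes the non-anaemic patients. Among the anaemic, iron deficiency stays unknown. A tick for iron in item 16 suggests the diagnosis, but only in treated patients, so untreated eligible patients remain hidden.

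**Size of the proxy bias for pre-operative standard 5 (illustration; every input is assumed).** Let c be true compliance among iron-deficient anaemic patients, p the share of anaemic patients who are iron deficient, and r the share of the other anaemic patients who receive iron. The all-anaemia rate is

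proxy = c x p + r x (1 - p)

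With c = 0.60 and r = 0:

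- p = 0.3: 0.60 x 0.3 = 18%
- p = 0.5: 0.60 x 0.5 = 30%
- p = 0.7: 0.60 x 0.7 = 42%

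Each is reported in place of 60%. The result depends on r. At r = 0.60 the proxy is 0.60p + 0.60(1 - p) = 60%, and the bias disappears.

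If 20-40% of 6000 patients were anaemic (also assumed), the true denominator would lie between 6000 x 0.20 x 0.30 = 360 and 6000 x 0.40 x 0.70 = 1680 patients.

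**Post-operative standard 2.** Because route is absent from item 4, the intravenous share among patients given iron in the index admission could be anything from 0 to 100%.

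**The case against.** The strongest reply is that haemoglobin is collected before admission, on admission and at several times after surgery, so most unaffected patients can be set aside. Item 16 records iron given before surgery, and pre-operative standard 5 names no route. A usable rate for that standard is therefore available if it is labelled as an anaemia proxy. This stands. A reader might infer that neither standard can be scored in any form, but the protocol does not support that. One practical condition applies: item 19 codes an absent pre-admission blood test as 0, so zeros must be treated as missing.

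A reader might also infer that the heading and the cited recommendation of post-operative standard 2 set conflicting denominators. They need not. The recommendation speaks of iron being indicated, not of iron being used, and the heading says in whom it is indicated. One gives the patients, the other the formulation.

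Nor does the protocol say that oral iron would count as compliant, or that all anaemic patients would form the denominator. Those would be an analyst's choices, and an analysis plan not shown here may address them. Any figure for how far intravenous use would be overstated would merely restate the oral share assumed.

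Finally, this is a descriptive audit without a powered comparison, and the anaemia secondary aim is served by haemoglobin. That limits the consequences. It does not supply the missing route or iron status.

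**Conclusion.** The point holds in two parts. First, the numerator of post-operative standard 2 is unavailable for the index admission, because route is not recorded. This follows from the text and needs no assumption. Second, neither standard's eligible group can be identified. Pre-operative standard 5 can be reported only against all anaemic patients, which counts untreated patients with other causes of anaemia as non-compliant.

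Two of nine components of the primary outcome are affected; the other seven are untouched by this point. The 18-42% range is illustrative and rests on 60% true compliance, a 30-70% iron-deficient share and no iron given to other anaemic patients. No figure in the protocol fixes any of these.

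Two limits apply. The live REDCap form is not shown and might hold more fields, although Appendix B is described as the full list. Also, pre-operative standard 5 speaks of iron being offered, whereas the form records iron given, so patients who declined would look like failures even with iron status known.

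**What to change.** Before data collection:

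1. Copy the oral/intravenous split of item 13 into post-operative item 4 and the matching Appendix A field.
2. Add an iron-deficiency field with the answers yes / no / not tested to the pre-operative and the post-operative sections.
3. Report compliance among patients answered 'yes', the proportion not tested, and, separately, an all-anaemia rate labelled as a proxy.
4. Align the two labels of item 4, so that collectors in all centres have the same patients in mind.

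The cost is three short fields, one label change and a little more data entry. Iron studies will be missing in some patients, so the 'yes' group will lean towards patients and centres that test; this must be stated as a limitation. If data have already been collected on the present form, report pre-operative standard 5 as a proxy and state that the intravenous criterion of post-operative standard 2 could not be assessed for the index admission.
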